12.1.1 Treatment-Emergent Adverse Event

A TEAE is defined as 1) a new event that occurs during or after treatment with study drug or 2) any event present at baseline that worsens in either intensity or frequency after exposure to study drug. If laboratory test abnormalities occur after the start of the administration of study drug, only clinically significant results will be considered to be TEAEs. Clinically significant cases are defined in section 6.2.1 of the protocol.

AEs that are checked "Post Dose" to the question 'Is this AE occurred before first administration?' in 'Adverse Event' page of the eCRF will be considered as TEAEs.

Total Number of TEAEs will be presented by actual treatment group. The number and percentage of subjects with at least one TEAE will be presented in total and by SOC, PT, relationship, intensity, and actual treatment group. The summary of TEAEs will be presented in alphabetical order of SOCs. Within each SOC, the PTs will also be presented in alphabetical order. At each level of summarization for the number of subjects with an event, a subject is counted only once if they reported one or more events and only the worst intensity will be counted. The following TEAE summaries will also be reported in separate tables.

- TEAEs considered to be related to study drug.
- TEAEs for at least 1% of subjects within PT among total treatment group.
- TEAEs with the intensity \geq Grade 3.

TEAEs considered to be related to study drug and TEAEs for at least 1% of subjects will be presented without relationship and intensity in summary tables.

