
Methodology: This is a Phase IIb, multicenter, placebo-controlled, randomized, double-blind, parallel-arm study to evaluate the efficacy and safety of 2 different doses of CT-P27 (45 mg/kg and 90 mg/kg) in subjects with acute uncomplicated influenza A infection. This proof-of-concept study will provide dose-ranging information for the subsequent clinical development of the drug.

No study procedures will be performed prior to informing the subject about the study and obtaining written informed consent. However, any test result which was obtained within the allowed screening period can be used as screening data for subject's convenience. It is critical that subjects receive treatment with study drug no more than 48 hours after the onset of symptoms (window of +12 hours is allowed). For most subjects, obtaining of the informed consent form (ICF), screening for eligibility, randomization, and treatment will occur on the same day. Though obtaining of the ICF may occur on the day prior to screening, randomization or treatment, it must be within 24 hours before the administration of study drug.

[figure not shown]
To be eligible for enrollment, subjects must have a positive test result for influenza A by a rapid influenza diagnostic test. At screening, nasopharyngeal swab samples will be collected for two times to be used for rapid influenza diagnostic test and virology assessment. The enrollment process is presented in [Figure S1](#).

Figure S1 Enrollment Process

Approximately 183 subjects with influenza A to be enrolled in the study will be randomly assigned to 1 of 3 groups, 45 mg/kg CT-P27, 90 mg/kg CT-P27, or placebo (70 subjects per CT-P27 treatment groups and 43 subjects in placebo group). Randomization will be stratified by flu vaccination history within a year (Yes vs No) and participation in PK sub-study (Yes vs No). A schematic diagram of subject assignment is presented in [Figure S2](#).

[figure not shown]
Figure S2 Schematic diagram of Subject Assignment

All enrolled subjects will be given a single dose of 45 mg/kg CT-P27, 90 mg/kg CT-P27, or placebo intravenously over 90 minutes (± 15 minutes) on Day 1 and then followed by Day 110.

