6.2 Safety Measures and Procedures

6.2.1 Definition of Adverse Events

An adverse event (AE) is defined as any untoward medical occurrence in a subject enrolled (i.e., when the ICF is signed) into this study regardless of its causal relationship to study drug. Subjects will be instructed to contact the Principal Investigator or sub-Investigator at any time after the ICF is signed if any symptoms develop.

An AE can therefore be any unfavorable and unintended sign (including an abnormal laboratory finding), symptom, or disease.

An AE includes a/an:

- a) Exacerbation of a pre-existing condition or disease.
- b) Increase in frequency or intensity of a pre-existing condition.
- c) Condition first detected or diagnosed after informed consent.

- d) Continuous persistent pre-existing disease or symptoms that worsen after the subject provides informed consent.

An AE does not include a/an:

- a) Medical or surgical procedure (e.g., surgery, endoscopy, tooth extraction, transfusion); the condition that leads to the procedure is an AE. Any complications of the procedure are also considered to be AEs.
- b) Pre-existing disease or conditions present or detected at the start of the study that do not worsen.
- c) Situations where an untoward medical occurrence has not occurred (e.g., hospitalizations for cosmetic elective surgery, social and/or convenience admissions).
- d) The disease or disorder being studied or signs or symptoms associated with the disease or disorder, unless more severe or frequent than expected for the subject's condition.
- e) Overdose of either study drug or concurrent medication without any signs or symptoms.

Medical history and any medical conditions that are present prior to informed consent will be recorded as medical history and not be reported as an AE.

Any signs and symptoms of influenza A infection throughout the study, including the screening period, will be captured on the Flu-iiQ™ and the body temperature in the diary.

A TEAE is defined as 1) a new event that occurs during or after treatment with study drug or 2) any event present at baseline that worsens in either intensity or frequency after exposure to study drug.

If laboratory test abnormalities occur after the start of the administration of study drug, only clinically significant results will be considered to be TEAEs. The clinically significant laboratory results include those that:

- Result in discontinuation from the study.

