6.2.1.4 Evaluation of AEs

Each AE is to be evaluated for duration, severity, seriousness, and causal relationship to the investigational drug. The action taken and the outcome must also be recorded.

Seriousness

The event will be evaluated to determine if it meets the criteria for an SAE, as described in [Section 6.2.1.1](#).

Severity/Intensity

The severity of the AE will be characterized according to the following criteria based on the Common Terminology Criteria for Adverse Events (CTCAE) v4.03:

- Grade 1 Mild; asymptomatic or mild symptoms; clinical or diagnostic observations only; intervention not indicated.
- Grade 2 Moderate; minimal, local or noninvasive intervention indicated; limiting age-appropriate activities of daily living.
- Grade 3 Severe or medically significant but not immediately life-threatening; hospitalization or prolongation of hospitalization indicated; disabling; limiting self-care activities of daily living.
- Grade 4 Life-threatening consequences; urgent intervention indicated.
- Grade 5 Death related to AE.

When evaluating an AE that recurs over time (for example, a specific AE reported multiple times in the diary), the Investigator will review the AE for changes in severity over the time period being assessed. The most severe grade will be assigned to that AE.

Relationship/Causality

The Investigator will assess the causality/relationship between the study drug and the AE and record that assessment in the eCRF. One of the following categories will be selected based on medical judgment, considering the definition below and all contributing factors. However, for the summarization of data, all categories other than unrelated will be considered as related to study drug.

- Definite: A clinical event, including laboratory test abnormality, occurring in a plausible time relationship to drug administration, and which cannot be explained by concurrent disease or other drugs or chemicals. The response to withdrawal of the drug (dechallenge) will be clinically plausible. The event must be definitive pharmacologically or phenomenologically, using a satisfactory rechallenge procedure if necessary.
- Possible: The relationship suggests that the association of the AE with the study drug is unknown; however, the AE is not reasonably supported by other conditions.

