6.4 Demographics and Medical History

At screening, information on demographics and background characteristics will be collected. The demographics include age, sex (male or female), and race (Caucasian, African, Asian, or Other). A general medical history (e.g., previous illnesses, current conditions, and family history, smoking habits) will also be collected. In addition, medical history of a subject can be newly added on the eCRF at any time point during the AE assessment period. Medical history is defined as a medical event or condition that will be recorded as part of the subject's medical history if the onset date of the event occurs before the ICF is signed. If a pre-existing medical event or condition recorded as medical history worsens after the ICF is signed, it would be reported as an AE, even if the onset date was prior to signing ICF.

The information will be recorded on the eCRF.

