12.1 Adverse Events

An adverse event (AE) is any untoward medical occurrence in a subject enrolled (i.e., when the ICF is signed) into this study regardless to its causal relationship to study drug. An AE can, therefore, be any unfavorable and unintended sign (including an abnormal laboratory finding), symptom, or disease.

All AEs will be classified by SOC and PT according to the MedDRA version 20.1 or later and the version number will be shown as a footnote on the corresponding tables and listings. AEs will be graded for intensity according to the Common Terminology Criteria for Adverse Events (CTCAE) v 4.03 ([Appendix 14.2](#)).

Listings for AEs occurring during the study will be provided by actual treatment received. The listing will include the following information from the eCRF: SOC, PT and reported term; Start date/time; End date/time; Whether the event is classified as TEAE or TEAE due to Infusion Related/Anaphylactic Reaction (IRR) (Yes, No); Duration of AE in days (Duration= [End date-Start date] +1); Frequency (continuous, intermittent, transient, other with specified frequency); Outcome (recovered, recovered with sequelae, recovering, not recovered, fatal, unknown); Intensity (Grade 1(mild), Grade 2(moderate) Grade 3(severe), Grade 4(life-threatening), Grade 5(death)); Relationship to study drug (Definite, Possible, Probable, Unrelated, Not assessable); Action taken with study treatment (No action taken, Dose reduce, IP interrupted, IP withdrawn, Other with specified action); Other treatment (No treatment, Medication treatment, Non-medication treatment with specified treatment, Both medication and non-medication treatment with specified treatment); Whether a subject terminated from study due to this AE (Yes, No); Whether the event is serious (Yes, No); Whether the event is classified as secondary complication (Yes, No).

Events will be considered to be related if relationship is definite, possible, probable or not assessable for the study drug.

A summary table of overall AEs will be presented by actual treatment group, including the following:

- Total number of AEs, SAEs
- Number and percentage of subjects with at least one AE, SAE, TEAE, TESA, TEAE leading to study discontinuation, TEAE due to IRR, TEAE leading to death.

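### The TEAE flag in SAP 12.1.1 has no route for an adverse event recorded as pre-dose that worsens after infusion, although the SAP's own TEAE definition includes such events

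*SAP*

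**What the plan says.** Protocol 6.2.1 and SAP 12.1.1 give the same two-part definition of a TEAE. The first part is a new event during or after treatment. The second is "any event present at baseline that worsens in either intensity or frequency after exposure to study drug".

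The next paragraph of SAP 12.1.1 says how the flag is set: AEs for which 'Post Dose' is checked "to the question 'Is this AE occurred before first administration?' in 'Adverse Event' page of the eCRF will be considered as TEAEs". The SAP gives no other derivation rule, and SAP section 13 lists no change to the TEAE definition.

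Four protocol statements determine what reaches that tick box:

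- Section 6.2.1 counts as an AE "Continuous persistent pre-existing disease or symptoms that worsen after the subject provides informed consent".
- Section 6.4 says of worsened medical history that "it would be reported as an AE, even if the onset date was prior to signing ICF".
- Section 6.2.1.4 deals with an AE that recurs over time: "The most severe grade will be assigned to that AE".
- Section 4.1 says of consent that "it must be within 24 hours before the administration of study drug", and section 6.2.1.5 collects AEs from the date of consent. An AE can therefore start before dosing.

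**The concern.** The definition has two parts and the rule implements one. The eCRF question concerns time of occurrence, so it identifies new events. It does not ask whether an event already present became worse or more frequent. For an AE that began before the infusion, the truthful answer is that it occurred before, and nothing later in the SAP brings it back if it worsens.

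TEAEs and TESAEs are named secondary safety endpoints (Protocol 8.2.3, SAP 3.2). The tables of related TEAEs, TEAEs of Grade 3 or higher, TEAEs in at least 1% of subjects, TESAEs, infusion-related TEAEs and TEAEs leading to study discontinuation all start from TEAE status. So does the line for TEAEs leading to death in the overall AE table. SAP 1.1 says that safety information will be used in choosing doses for later studies. If a dose aggravated events already present at infusion, these tables could understate the difference from placebo.

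**Working it through.** The plan states no figure to reproduce. The check is whether definition and flag agree for each kind of event under the recording rules above.

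1. **New event after the infusion starts.** The definition includes it and 'Post Dose' is ticked. They agree.
2. **Pre-dose AE that does not worsen.** The definition excludes it and it is not ticked. They agree.
3. **Medical history that worsens after infusion, with the site answering from the time of worsening.** The second part of the definition includes it and 'Post Dose' is ticked. They agree.
4. **The same event, with the site answering from the original onset.** The definition includes it but it is not flagged. They disagree. Protocol 6.4 requires the AE report but does not say which onset date or tick the record carries.
5. **AE that starts between consent and infusion, worsens after infusion and stays one record.** The definition includes it, but the correct answer to the question is that it occurred before dosing, so it is not flagged. They disagree whatever the site's reading.
6. **The same event, with the worsening entered as a new record.** It is flagged, so they agree. Neither document tells sites to open a new record. The one rule close to this, in Protocol 6.2.1.4, gives a recurring AE a single worst grade.

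The mismatch is therefore certain in case 5 and possible in case 4.

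Two further checks show whether the plan recovers these events elsewhere:

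- The AE listing in SAP 12.1 carries start and end date/time, one intensity and the TEAE classification. It lists neither the grade at dosing nor the date of worsening, so the second part of the definition cannot be derived from those variables.
- The SAP assigns to the blinded Data Review Meeting the analysis populations and protocol deviations (section 6), symptom-relief drugs (10.1), anti-infectives (10.2, 14.4) and infusion-reaction coding (12.1.1.2). TEAE classification is not on the list.

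For scale only, at the planned sizes of 70 per dose arm and 183 in total:

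- One missed subject in a dose arm: 1/70 = 0.014, or 1.4 percentage points.
- Threshold for the 1% table: 0.01 × 183 = 1.83, so a preferred term needs 2 subjects. If one of those two is missed, 1/183 = 0.5% remains and the term leaves that table.

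These figures show what a single event is worth. They do not estimate how many are missed.

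**The case against.** A reader might infer that every pre-existing condition that flares after infusion drops out of every TEAE table. The documents do not support that, for four reasons.

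- The SAP does not say that only ticked events are TEAEs. It states the full definition and then says that ticked events count. Exclusivity is an inference from the absence of any other rule.
- Under Protocol 6.2.1 the AE is the exacerbation itself. For a controlled condition that flares after the infusion, no AE exists until the flare, so 'Post Dose' is a natural answer. Section 6.4 makes the event reportable and does not send it to the pre-dose side.
- The worst-grade rule in Protocol 6.2.1.4 is about severity, with repeated diary reports as its example, and the diary starts only on Day 1. It does not address onset dates or the tick. Its relevance is limited to the fact that it does not split a record when an event worsens.
- The certain window is short, and for most subjects consent and dosing fall on the same day. Influenza symptoms, probably the commonest complaints in that window, are not AEs unless worse than expected and are recorded on the Flu-iiQ.

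Nor would a missed event vanish from safety reporting. It stays in the AE and SAE listings and in the overall AE and SAE counts. Depending on its nature, it may also show in the secondary-complication summary, which has its own eCRF flag, or in the suspicious-ADE, vital-sign, ECG, laboratory, physical-examination or chest X-ray outputs.

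All of this stands, and it narrows the point. None of it supplies a rule for the second part of the definition. The eCRF and its completion instructions might settle how sites answer, but they are not among the documents.

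**Conclusion.** The point holds in narrow form. The stated flag does not implement the second part of the SAP's own TEAE definition. An AE recorded as occurring before dosing that worsens after infusion, and is kept as one record, can be missed in the TEAE-based tables. This is certain for AEs starting between consent and infusion. For worsened medical history it depends on how the site reads the question.

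The number of affected events is probably small and cannot be derived from the documents. The conclusion assumes that the tick is applied as written, that no unseen completion guide tells sites to enter worsening as a new 'Post Dose' record, and that no further programming rule exists. It is still more than a missing detail, because the rule as written misclassifies events against the plan's definition in named secondary endpoints.

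**What to change.** In SAP 12.1.1, define the flag as any AE ticked 'Post Dose', or any AE with earlier onset whose intensity or frequency increased after the start of infusion. Add to the agenda of the blinded Data Review Meeting a check of all AEs not ticked 'Post Dose' for post-infusion worsening, and document the decisions before unblinding.

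The cost is a sentence in the SAP and a short blinded review of what should be few records. Because the listed variables hold one intensity and no date of worsening, some records may need a query to the site. TEAE counts may rise slightly.

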12.1.1.1 Treatment-Emergent Adverse Events Leading to Study Discontinuation

TEAEs that are checked "Yes" to the question 'Did the adverse event cause the subject to be discontinued from the study?' in the 'Adverse Event' page of the eCRF will be considered as TEAEs leading to study discontinuation.

TEAEs leading to study discontinuation will be presented in a table in a similar manner to the tables of TEAEs described in section 12.1.1. Also, TEAEs leading to study discontinuation will be listed including the variables detailed in section 12.1 except whether a subject terminated from study due to this AE (Yes, No).

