5.4 Precautions and/or Overdose

There are no specific antidotes to CT-P27. Treatment of an overdose should be symptomatic.

Subjects who develop severe infusion-related reactions must have infusion terminated immediately, and the subject will be treated according to the best standards of care. These subjects will be followed up until stabilized, or until the reaction resolves.

During infusion of study drug, emergency drugs and equipment suitable for assistance during anaphylactic reactions will be available during infusion with study drug.

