8.2.3 Secondary Safety Endpoints

The following safety parameters are secondary endpoints:

- Treatment-emergent adverse events (TEAEs)
- Treatment-emergent serious adverse events (TESAEs)
- TEAEs leading to treatment discontinuation
- Clinical laboratory analyses (hematology, biochemistry, and urinalysis laboratory tests)
- Vital sign measurements
- ECGs
- Physical examination findings

- Evaluation of ADE throughout the entire study duration. For the definition of suspicious ADE, please see [Section 6.2.5](#).

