8.5.4 Safety Analyses

The safety analysis will be performed on the safety population at the time points specified in [Table 1](#) by presenting data on TEAEs, TESAEs, TEAEs leading to treatment discontinuation, clinical laboratory analyses, vital signs, ECG, physical examination, suspicious ADE, and other safety evaluations.

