8.5.4.1 Adverse Events

Adverse events will be graded for severity and the terminology of AEs will be described according to the CTCAE v4.03. All safety data will be listed and summarized by treatment group as appropriate.

Adverse events will be coded to system organ class (SOC) and preferred term (PT) according to MedDRA.

The following TEAE summaries will be reported by SOC, PT, and treatment group:

- Number and percentage of subjects reporting at least one TEAE by SOC and PT
- Number and percentage of subjects reporting at least one TESAЕ by SOC and PT
- Number and percentage of subjects reporting at least one TEAE leading to treatment discontinuation by SOC and PT

Treatment-emergent AEs will also be summarized by maximum severity and relationship to study drug with the percentage of subjects in each category. If more than one TEAE is recorded for a subject within any SOC or PT, the subject will only be counted once using the most severe assessment.

The number and percentage of subjects with suspicious TEADE will be presented by treatment group.

8.5.4.2 *Clinical Laboratory Evaluations*

Clinical laboratory tests (hematology, biochemistry, and urinalysis) will be summarized, by treatment, at each scheduled collection time. For continuous parameters, change from baseline will also be summarized for all scheduled collection times after the first infusion. Clinical laboratory data will also be summarized using shift tables for categorical parameters.

All laboratory results will be listed.

8.5.4.3 *Vital Signs Measurements, Physical Findings, and Other Safety Evaluations*

Vital signs of SBP, DBP, heart rate, and respiration rate will be summarized by treatment group, at each scheduled collection time. Changes from baseline will also be summarized by treatment group.

The number and percentage of subjects with abnormalities in vital signs or ECG during the infusion and immediate post-infusion period will be summarized by time point and treatment group.

Physical examination results will be summarized by counts and percentages at each scheduled collection time. In addition, shift tables will be presented.

Electrocardiogram parameters will be summarized by counts and percentages, at each scheduled collection time. In addition, shift tables will be presented.

8.5.5 *Subject Baseline Characteristics*

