3.2 Safety Endpoints

The following safety parameters are secondary endpoints:

- Treatment-emergent adverse events (TEAEs)
- Treatment-emergent serious adverse events (TESAEs)
- Clinical laboratory analyses (hematology, biochemistry, and urinalysis laboratory tests)
- Vital sign measurements
- Immediate hypersensitivity monitoring
- Electrocardiograms (ECGs)
- Physical examination findings
- Weight assessment
- Pregnancy test
- Chest X-ray
- Evaluation of ADE throughout the entire study duration

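### The SAP replaces the protocol's table of adverse events that stop treatment with one of adverse events that end study participation, and does not record the change

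*SAP*

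**What the plan says.** **Protocol.** Section 8.2.3 names "TEAEs leading to treatment discontinuation" as one of eight secondary safety parameters. Section 8.5.4 repeats it in the scope of the safety analysis: "by presenting data on TEAEs, TESAEs, TEAEs leading to treatment discontinuation, clinical laboratory analyses". Section 8.5.4.1 specifies the output, to be given by treatment group: "Number and percentage of subjects reporting at least one TEAE leading to treatment discontinuation by SOC and PT". Section 8.3 commits the SAP to documenting any departure from the analyses planned in the protocol.

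**SAP.** Section 3.2 does not list the endpoint. The overall adverse-event summary in 12.1 ends with "TEAE leading to study discontinuation, TEAE due to IRR, TEAE leading to death". Section 12.1.1.1 selects events by an eCRF question on whether the event took the subject out of the study, then states: "TEAEs leading to study discontinuation will be presented in a table in a similar manner to the tables of TEAEs described in section 12.1.1". In the table list (14.7), Table 14.3.1.6 is the only adverse-event table about discontinuation, and it concerns the study. The eCRF also records what was done with the study drug. Section 12.1 carries this as a listing variable: "Action taken with study treatment (No action taken, Dose reduce, IP interrupted, IP withdrawn, Other with specified action". Section 13 lists seven changes from the protocol, and this is not among them.

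**The concern.** Where treatment is given repeatedly, stopping treatment and leaving the study often coincide, and one count may roughly stand in for the other. Here each subject receives one infusion over about 90 minutes and is then followed to Day 110. Treatment can be discontinued only while the infusion is running, whereas participation can end at any time in the following months. Protocol 5.4 expressly provides for the first case: "Subjects who develop severe infusion-related reactions must have infusion terminated immediately". It then describes follow-up of those subjects and does not say that they leave the study.

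At stake is a prespecified safety comparison. The trial is meant to inform dose selection, and Protocol 2.4.1 uses slow infusion to limit infusion-related reactions. How often an adverse event stopped the infusion at 45 mg/kg, at 90 mg/kg and on placebo is a question the protocol undertook to answer in a table. The SAP as written does not answer it there.

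**Working it through.** The plan gives no figure to reproduce, so the check is a comparison of text.

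**1. Endpoint lists.** Protocol 8.2.3 has eight items. SAP 3.2 has eleven. Seven of the protocol's eight are carried over, and four are new: immediate hypersensitivity monitoring, weight, pregnancy test and chest X-ray. The missing one is treatment discontinuation.

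**2. Adverse-event tables.**

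| Protocol 8.5.4.1, by SOC, PT and group | SAP counterpart |
|---|---|
| Any TEAE | 12.1.1, Table 14.3.1.2 |
| Any serious TEAE | 12.1.2, Table 14.3.2.1 |
| TEAE leading to treatment discontinuation | None; 12.1.1.1 and Table 14.3.1.6 cover study discontinuation |

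No table in SAP 14.7 is keyed to withdrawal of study drug.

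**3. Are the two events the same?** The eCRF keeps them apart: SAP 12.1 lists the action taken with study treatment and, as a separate variable, whether the subject left the study because of the event. Cross-classifying the two gives:

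| | Left study because of event | Stayed in study |
|---|---|---|
| Infusion stopped for event | In both counts | Protocol count only |
| Infusion not stopped for event | SAP count only | In neither |

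The two off-diagonal cells are where the measures part. A subject in the top right cell is missing from Table 14.3.1.6. A subject in the bottom left cell is in that table without having discontinued treatment.

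**4. Where a top-right subject would still appear.**
- The general TEAE table (SAP 12.1.1), without any sign that the infusion was stopped.
- The infusion-reaction tables (12.1.1.2), if the investigator classifies the event that way.
- The Grade 3 or higher table (12.1.1), if graded so.
- The exposure table (9.2), as a partial dose by treatment group, without the reason, if the full dose was not given.
- The adverse-event listing, line by line, with the action taken.

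None of these gives the number and percentage of subjects, by arm and by SOC and PT, in whom an event led to the infusion being stopped.

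**5. Scale.** The denominator is the safety population, planned at about 70 per CT-P27 arm and 43 on placebo (Protocol 4.1). The 63 per CT-P27 arm in Protocol 8.1 is the eligible infected number and does not apply to safety tables. One subject is 1/70 = 1.4% of a CT-P27 arm, or 1/43 = 2.3% of the placebo arm. This shows only what one missed case is worth, since the documents state no expected rate of stopped infusions.

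**6. Change record.** The seven items in SAP Section 13 cover the scope of the first report, the ITT definition, the safety population definition, the tipping-point analysis, values below the limit of quantification, the AUC extrapolation rule, and the added sensitivity analyses of the primary endpoint. None concerns this endpoint.

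**The case against.** The best defence is that little is hidden. A severe infusion reaction would be expected in the infusion-reaction and Grade 3 or higher tables, an incomplete infusion is counted as a partial dose by arm, and the action taken can be read for every event in the listing. The SAP also adds immediate hypersensitivity monitoring as a safety endpoint. All of that stands. A reader might infer that stopped infusions would show as zero throughout the summary tables. The documents do not support this: only the study-discontinuation row and Table 14.3.1.6 could show none.

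A reader might also infer that every subject whose infusion is stopped remains in the study and is answered No to the SAP's selecting question. That goes too far as well. Protocol 5.4 speaks of follow-up until the subject is stabilized or the reaction resolves, not of continuing to Day 110, and neither document says how the eCRF item is completed in this situation. Some such subjects may be recorded Yes. The supportable statement is that they could be missed.

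Finally, the endpoint is descriptive, is one of eight that the protocol does not rank, and has no bearing on the primary analysis. This is fair, and it limits the weight of the point. It does not explain why a named endpoint and its table were dropped without an entry in Section 13.

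**Conclusion.** The point holds as an undocumented change to a prespecified safety table. If the SAP is followed as written, the protocol's count of subjects with an adverse event that stopped treatment will not be reported by arm. The gap is in tabulation; the data are collected and listed. Its size depends on how many infusions are stopped for an event in subjects who then stay in the study, which cannot be known in advance; each such subject in a CT-P27 arm is about 1.4%.

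The conclusion rests on two readings: that treatment discontinuation in a single-infusion trial means the infusion was stopped before completion, and that IP withdrawn is the eCRF category that records this. An interruption is a different matter. Protocol 8.4.4 and SAP 5.3 count an interrupted infusion as a complete dose if the full amount is given, so interruptions are not part of this endpoint. The change should be made, but it is of modest weight and does not touch efficacy.

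**What to change.** Restore the endpoint in SAP 3.2. In 12.1.1, add one table by SOC, PT and actual treatment group of TEAEs whose action taken is IP withdrawn, with a matching row in the overall adverse-event summary in 12.1. Keep Table 14.3.1.6, which is useful in its own right, and enter it in Section 13 as an addition to the protocol analysis. At the blinded data review, confirm that IP withdrawn captures infusions stopped for an event by comparing it with the partial-dose records.

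The cost is one table and one row from a field already on the adverse-event page. Data collection, conduct and sample size are unaffected. If the SAP can no longer be amended, SAP 5.1 allows the added table to be justified and recorded in the study report.
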